6.2 Brachytherapy Treatment Planning

- 6.2.1 CT Simulation: CT simulation will be performed per standard protocol for evaluation of catheter position and treatment planning.
- 6.2.2 Diagnostic MRI: When possible, patient will undergo a diagnostic MRI after the implant with the catheters in position to aid in treatment planning. This will be registered to the CT image set.
- 6.2.3 Volume delineation: Target volumes and organs at risk (OARs) will be contoured using brachytherapy planning software. The patient's prior multi-parametric MRI and the fiducial placed during the procedure can be used to help define the target.
- 6.2.4 Source Loading: The HDR treatment will be delivered on the day of the catheter placement, after visual inspection of the catheters prior to delivery of the treatment is performed, and any necessary catheter adjustments are made prior to the treatment. If the catheters cannot be satisfactorily repositioned and cannot be corrected by a new plan with appropriate coverage of the target and sparing of the OARs, then we will consider postponing or aborting the treatment

6.3 Brachytherapy Volume Delineation:

- 6.3.1 Target Volume: The target volume will consist of the prostate and proximal seminal vesicles encompassing the area of local recurrence. The Planning Target Volume (PTV) will be defined as the GTV, plus a 0-5 mm margin, restricted to adjacent OARs applicable.
- 6.3.2 Critical Structures: Critical structures to be contoured include the bladder, Foley bulb, rectum, and urethra. Critical structures must be contoured on every CT slice that contains a target volume and in at least 3 slices (9 mm) above and below the CTV

6.4 Brachytherapy Dose Specifications:

- 6.4.1 For each brachytherapy procedure, the prescription dose to the PTV and GTV will be the highest deliverable dose up to 12 Gy in one fraction. Priority will be given to the normal tissue dose constraints over the

prescription dose. That is, the maximum dose will be that which is achievable without violating the normal tissue dose constraints. Priority will be given to GTV coverage first and then CTV coverage. If necessary, treatment to areas of the prostate/seminal vesicles judged to be at low risk of involvement can be omitted if it is felt that delivering full dose to these areas would result in unacceptable significant risk of toxicity.

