9.0 MEASUREMENT OF EFFECT

9.1 *Antitumor Effect- Solid Tumors*

9.1.1 Definitions:

Evaluable for toxicity: All patients will be evaluable for toxicity immediately following brachytherapy.

Evaluable for disease control assessment: All patients with at least 2 follow-up PSAs will be evaluable for disease control. After brachytherapy, these patients will have their disease status classified according to the definitions stated below.

Biochemical (PSA) recurrence (BR): Based on RTOG Phoenix definition: an increase of the PSA level at least 2 ng/ml greater than the minimum level after therapy (REF: phoenix paper)

All patients with BR should undergo at least MP-MRI of the prostate and bone scan. Biopsy of any suspicious lesions within the prostate gland on MP-MRI is encouraged.

Freedom from Biochemical (PSA) Recurrence (FFBR):

The time to PSA failure will be measured from the date of treatment to the date of a rise by 2 ng/mL or more above the nadir PSA. The time of failure will be the date of the first PSA that is 2 ng/mL or more above the lowest prior post-treatment PSA value. If the rise in PSA to $>$ nadir + 2 occurs during the first 36 months followed by a subsequent non-hormonal induced PSA decrease, patients will **not** be considered PSA failures.

As a benign “spike” or “bounce” in the PSA value has been described in as many as 35% of patients 12-36 months following brachytherapy, intervention for a PSA failure should be based on a positive prostate biopsy at least 24 months post-treatment and/or clinical evidence of distant relapse (i.e., bone scan, CT scan, etc).

Local Failure (LF): This rating will be assigned when there is biopsy-proven disease progression or recurrence at the lesion within the prostate treated with protocol therapy. Histologic criterion for local failure is the presence of prostatic carcinoma upon biopsy more than 2 years after the start of treatment. Residual carcinoma on biopsy should show minimal radiation effect and should be in clinical scenario of increasing PSA.

Local Control (LC): Absence of local failure. This will be assumed in patients with a controlled PSA and for those with PSA failure but no radiographic, clinical, or biopsy-proven disease at the lesion treated with protocol therapy.

Freedom from Local Failure (FFLF): The time to local progression will be measured from the date of treatment to the date of local failure.

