Elsewhere Prostate Failure (EPF): This rating will be assigned when there is biopsy-proven disease progression/recurrence at outside the lesion treated with protocol therapy but within the prostate or seminal vesicles.

Elsewhere Prostate Control (EPC): Absence of EPF. Will be assumed in patients with a controlled PSA and in patients with PSA failure but no radiographic, clinical, or biopsy-proven disease at the site treated with protocol therapy.

Freedom from Elsewhere Prostate Failure (FFEPF): The time to elsewhere prostate failure will be measured from the date of treatment to the date of EPF.

Regional Failure (RF): Visible disease on imaging that occurs in lymph nodes within the usual regional spread pattern of prostate cancer

Regional Control (RC): Absence of regional/nodal recurrence.

Freedom from Regional Failure (FFRF): The time to regional failure will be measured from the date of treatment to the date of RF.

Distant Metastasis (DM): Visible disease on imaging that occurs elsewhere in the body including non-regional lymph nodes.

Freedom from Distant Metastasis (FFDM): The time to distant metastasis will be measured as the date of treatment to the date of DM.

Freedom from hormone therapy (FFHT): The time from the date of treatment to first administration of androgen deprivation therapy

Disease-free Survival (DFS): Defined as the duration of time from the date of completion of treatment to either BR, LF, EPF, RF, DM, or death.

Cause-specific Survival (CSS): Defined as the duration of time from the date of completion of treatment to death from prostate cancer.

Overall Survival (OS): Defined as the duration of time from the date of completion of treatment until death from any cause.

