12.0 STATISTICAL CONSIDERATIONS

12.1 *Study Design/Study Endpoints*

The primary outcome will be any radiotherapy-related acute or chronic grade 3-5 toxicity as defined previously in the document. The study is designed as a two stage Phase II study as described below.

12.2 *Sample Size and Accrual*

Primary Aim

In this single-arm oncology trial evaluating the safety and efficacy of HDR brachytherapy for recurrent prostate cancer, one goal is to determine the toxicity

of single fraction focal treatment. Simon's two-stage²³ design is used to power this aim. The primary hypothesis is that the acceptable toxic response rate is less than or equal to 10.0% (p_1). The unacceptable toxic rate is set at 33% (p_0).

More concisely:

$$H_0: p_0 \geq .33$$

$$H_A: p_1 \leq .10$$

The null hypothesis is that the unacceptable toxic response rate is at least 33%. This will be tested against a one-sided alternative that the toxicity rate is 10% or less.

In the first stage, 7 patients will be accrued. If there are 2 or more toxic responses (radiation-related acute grade ≥ 3 GU or GI toxicity) in these 7 patients, the study will be stopped for safety reasons. Otherwise, 17 additional patients will be accrued for a total of 24 patients. Note that, under these conditions, the probability of stopping early is 73% if the toxic response rate is truly higher than 10.0%.

At the end of the second stage, the null hypothesis that the toxicity rate is 33% or higher will be rejected if more than 19 (non-toxic) responses are observed in 24 patients. When the true toxicity rate is 10.0%, this design yields a type I error rate of .046 and power of 81%.

Secondary Aim

We also will describe the freedom from biochemical recurrence, relapse-free survival, local control, elsewhere-prostate control, freedom-from local failure, freedom from distant metastasis, freedom from hormonal therapy, disease-free survival, cause-specific survival, and overall survival.

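### In section 9.1.1 the two sentences defining Elsewhere Prostate Control contradict each other, because the second checks the treated site instead of the rest of the prostate

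*Combined protocol and SAP*

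**What the plan says.** The relevant definitions are in section 9.1.1.

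- **Elsewhere Prostate Failure (EPF):** "biopsy-proven disease progression/recurrence at outside the lesion treated with protocol therapy but within the prostate or seminal vesicles".
- **EPC, first sentence:** "Elsewhere Prostate Control (EPC): Absence of EPF".
- **EPC, second sentence:** control is assumed in two groups. One is men with a controlled PSA. The other is men with PSA failure but "no radiographic, clinical, or biopsy-proven disease at the site treated with protocol therapy".
- **Local Control:** assumed with a controlled PSA, and in men with "PSA failure but no radiographic, clinical, or biopsy-proven disease at the lesion treated with protocol therapy".
- **Freedom from EPF:** "The time to elsewhere prostate failure will be measured from the date of treatment to the date of EPF".

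Section 12.2 names the outcome among those to be described under the secondary aim: "local control, elsewhere-prostate control, freedom-from local failure". The Statistical Methodology entry in the Study Summary gives the same list.

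**The concern.** EPF and local failure are meant to separate recurrence away from the treated lesion from recurrence at it. The second EPC sentence matches the Local Control clause except that it says site where Local Control says lesion. It looks like a clause carried over without changing the location.

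The first EPC sentence points outside the treated lesion and the second points at it. Section 9.1.1 says disease status will be classified by these definitions, but not which sentence prevails. Two assessors could therefore reach opposite EPC ratings for the same man, and the men affected are those whose disease is confined to one of the two locations. No other section corrects the clause.

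**Working it through.** The plan gives no figure to reproduce here, so the check is logical. Three facts about a patient matter: PSA failure (yes/no), disease at the treated lesion (yes/no), and biopsy-proven disease elsewhere in the prostate or seminal vesicles (yes/no). That gives 2 × 2 × 2 = 8 patterns.

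Rules compared:

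- **First sentence:** EPC if there is no biopsy-proven disease elsewhere.
- **Second sentence as written, site = treated lesion:** EPC assumed if PSA is controlled, or if PSA has failed and there is no disease at the lesion.
- **Second sentence as written, site = whole brachytherapy target:** as above, but disease anywhere in the target blocks the assumption. Section 6.3.1 makes this reading possible: "The target volume will consist of the prostate and proximal seminal vesicles encompassing the area of local recurrence". Elsewhere disease is taken here to lie inside the target.
- **Second sentence with the location changed:** EPC assumed if PSA is controlled, or if PSA has failed and there is no disease elsewhere.

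**Patterns with PSA failure**

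| Disease found | EPF? | First sentence | Second: site = lesion | Second: site = whole target | Second: location changed |
|---|---|---|---|---|---|
| Neither place | No | EPC | Assumed | Assumed | Assumed |
| Elsewhere only | Yes | Not EPC | Assumed (**conflict**) | Not assumed | Not assumed |
| Treated lesion only | No | EPC | Not assumed (**conflict**) | Not assumed (**conflict**) | Assumed |
| Both places | Yes | Not EPC | Not assumed | Not assumed | Not assumed |

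**Patterns with controlled PSA.** The second sentence assumes EPC in all four under every version. It conflicts with the first sentence in the two patterns that have biopsy-proven disease elsewhere.

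**Conflicting patterns**

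| Version | PSA failure | Controlled PSA | Total |
|---|---|---|---|
| As written, site = lesion | 2 of 4 | 2 of 4 | 4 of 8 |
| As written, site = whole target | 1 of 4 | 2 of 4 | 3 of 8 |
| Location changed | 0 of 4 | 2 of 4 | 2 of 8 |
| Location changed, and proven EPF overrides | 0 of 4 | 0 of 4 | 0 of 8 |

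These are counts of logical patterns, not of patients. The controlled-PSA conflict is probably uncommon in practice, because the section 8.3 schedule calls for MP-MRI after baseline only at biochemical recurrence.

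**Where the EPC rule is used.** Section 2.3.2.4 lists freedom from EPF as the secondary endpoint, and section 9.1.1 times it to EPF. The disease-free survival definition also takes EPF as a component. Neither uses the second EPC sentence. Only the elsewhere-prostate control outcome in section 12.2 and the Study Summary does.

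**The case against.** The strongest reply is that the first sentence already gives the right answer in both conflicting PSA-failure patterns. The EPF definition assigns a rating on biopsy proof. The second EPC sentence speaks only of assuming control, which reads naturally as a default where failure has not been shown. A man with a positive biopsy elsewhere already has EPF, so nothing is left to assume. This stands to the extent that misclassification is possible, not certain. It does not remove the fault, because the text sets no order of precedence and the second sentence is the one that tells an assessor where to look.

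Two further replies stand in part.

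- **A local-only failure is never called uncontrolled.** The sentence says when EPC is assumed, not when it is denied. What can be said is that the assumption is withheld from a man who meets the first sentence.
- **Site may mean the whole treated target.** On that reading the elsewhere-only conflict largely goes. The local-only conflict remains, and so does the elsewhere-only conflict for seminal vesicle disease beyond the proximal part. The reading is also uncertain, since the neighbouring EPF definition ties treatment to the lesion.

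A reader might infer that every man with PSA failure and disease at only one location will be misclassified, or that EPC simply reproduces Local Control. Both hold only if the first sentence is ignored and site is read as lesion. The documents do not require either step.

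**Conclusion.** The contradiction is real and should be corrected. With site read as the treated lesion, the two EPC sentences disagree in two of the four PSA-failure patterns. With site read as the whole target, they disagree in one. Actual misclassification depends on the second sentence being the one applied.

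The reach is narrow: one descriptive outcome, for which section 12.3 specifies no test. Freedom from EPF, disease-free survival, the primary toxicity endpoint, the stopping rule and the sample size are unaffected.

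The number of patients affected cannot be stated, because the documents give no expected count of PSA failures by location. A reader might put the effect at 1/24 = 4.2 percentage points per man. That assumes full accrual and all 24 evaluable, whereas section 9.1.1 requires at least two follow-up PSAs for disease control and section 12.2 allows stopping after 7 patients (1/7 = 14.3 points per man). Either figure is the weight of one patient in a crude rate, not an estimate of error.

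**What to change.** Make two changes to the EPC definition in section 9.1.1.

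1. In the PSA-failure clause, replace the reference to the treated site with the location used for EPF: anywhere in the prostate or seminal vesicles other than the treated lesion.
2. Add that biopsy-proven EPF overrides any assumed control, including in a man with a controlled PSA. The first change alone leaves that branch in conflict.

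One difference would remain. EPF needs biopsy proof, whereas the EPC clause also counts radiographic and clinical disease, and biopsy of a suspicious MP-MRI lesion is only encouraged. A man with PSA failure and unbiopsied disease elsewhere would have no EPF but would not be assumed EPC. A sentence saying how he is reported would close this.

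The cost is a short wording amendment made before disease status is classified. It needs no new data and no change to assessments or sample size.

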Diagnosis and Main Inclusion Criteria	
 • Biopsy-proven local recurrence of prostate adenocarcinoma (biopsy within 182 days) • Pathologic Fluciclovine uptake in pelvic lymph nodes without distant metastases • Current AUA International Prostate Symptom Score (IPSS) score <20 • Initial disease stage cT1-3a NX or N0 • Treated with prior definitive radiation therapy using any radiotherapeutic modality (prior whole pelvis RT ineligible)
Duration of Administration	2 brachytherapy implants, ~5-8 weeks of daily radiation, 6 months hormonal therapy
Statistical Methodology	
This study is designed as a two stage Phase I/II, non-randomized study. In the first stage, 7 patients will be accrued. If there are 2 or more toxic responses in these 7 patients, the study will be stopped for safety reasons. Otherwise, 17 additional patients will be accrued for a total of 24 patients.
 
Assuming that the true toxicity rate in the population is 10% or less, the study is powered to reject the null hypothesis that the toxicity rate is 33% or higher. A toxicity event is defined as an acute grade ≥ 3 radiation-related toxicity as assessed by the Common Toxicity Criteria for Adverse Events version 4.
 
Standard non-parametric or parametric methods will be used to describe these patients' demographic and clinical information as well as their dosimetric information. The primary aim of the study is to estimate the toxicity rate of HDR brachytherapy among patients with recurrent prostate cancer. A one-tailed test for a difference in proportions will be used to determine whether the observed toxicity rate is lower than the hypothesized toxicity rate. The null hypothesis that the toxicity rate is 33% or higher will be rejected if more than 19 (non-toxic) responses are observed in 24 patients. When the true toxicity rate is 10.0%, this design yields a type I error rate of .046 and power of 81%.
 
We also will describe the freedom from biochemical recurrence, relapse-free survival, local control, elsewhere-prostate control, freedom-from local failure, freedom from distant metastasis, freedom from hormonal therapy, disease-free survival, cause-specific survival, and overall survival.

Study Schema

LU 210546

Version 10/23/17

Table of Contents

Title page.....	i
Signature page.....	iv
Study Summary.....	v-vi
Study Schema	vii
List of Abbreviations	x
1.0 Background and Rationale	1
1.1 Disease Background and Lessons from Other Malignancies	1

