2.3.2.9 Disease-specific survival

2.3.2.10 Overall Survival.

- 2.3.2.11 Patient reported Health-related quality of life as measured by the IPSS and EPIC-26 assessments (see Appendices B and C).
- 2.3.3 NCI CTCAE v4.03 toxicity criteria will be used to assess acute and late adverse events/toxicity endpoints (Appendix A). Disease specific endpoints will utilize a combination of laboratory values, multidisciplinary clinical decisions, radiographic imaging, functional imaging, and initiation of salvage therapy.

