6.0 RADIATION THERAPY

RT will start ~2 months after the start of ADT when possible (with RT starting earlier or later based on physician discretion). Either Brachytherapy or EBRT can be delivered first, or brachytherapy can be intercalated with EBRT course based on treating physician discretion.

6.1 *Brachytherapy Implant procedure:*

6.1.1 Patients will undergo 2 implants with 1 fraction of 12 Gy delivered with each implant, scheduled 1-2 weeks apart when possible, although longer or shorter intervals are acceptable with PI approval.

6.1.2 The implant procedure will be done under general anesthesia. The patient should be placed in the lithotomy position, generally after appropriate anesthesia. Then the perineum will be prepped and draped. A Foley catheter should be inserted for better visualization of the urethra and the bladder for the duration of the implant. Then, a single fiducial marker should be placed in the area of the target lesion as close to the lesion center as possible. Then, the brachytherapy loading catheters should be placed with the aid of a Liberty Medical template to allow for at least adequate coverage of the target lesion. Once adequate placement is confirmed by transrectal ultrasound (TRUS), the template will be sutured to the perineum. The patient's legs should be returned to a neutral position. After the patient is awoken from anesthesia and has stabilized, he will then be transferred to the Radiation Oncology Department for CT simulation, treatment planning, and radiation delivery.

- 6.1.3 Patient controlled analgesia (PCA), IV, or PO pain medications may be used during the post-operative period for pain control and throughout the day of the procedure as needed.
- 6.1.4 After completion of each of the brachytherapy treatments (upon completion of MRI and Treatment planning), all catheters should be removed.

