7.0 HORMONE THERAPY

Other than androgen deprivation therapy, patients must not receive other cancer-directed therapy (including standard fractionated radiotherapy, chemotherapy, biological therapy, and surgery) while on-study except at disease progression.

Standard institutional practices for neoadjuvant/concurrent and adjuvant short-term (6 months) androgen deprivation hormonal therapy will be used with the salvage

radiotherapy regimen. When possible, radiotherapy will begin approximately 2 months after the start of hormonal therapy. Some patients may have received prior hormonal therapy, but still require 6 months with the trial.

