7.2 LHRH Agonist Therapy (leuprolide, goserelin)

For additional information, consult the package inserts.

- 7.3.1 Timing: The first LHRH administration will occur together with the start of anti-androgen treatment ~8 weeks prior to the start of RT. The total duration of LHRH therapy will be 6 months. The total administered duration as well as the specific agent used must be documented.
- 7.3.2 Description: LHRH agonists are long-acting analogs of the native LHRH peptide and are effective at reducing serum testosterone. Analogs approved by the FDA (or by Health Canada for Canadian institutions) can be used in this study.
- 7.3.3 Supply: Commercially available.
- 7.3.4 Storage: LHRH analogs should be stored as directed by the commercial supplier.
- 7.3.5 Administration: LHRH analogs are administered with a variety of techniques, including subcutaneous insertion of a solid plug in the abdominal wall (Zoladex), intramuscular injection (Lupron), subcutaneous injection (Eligard), or insertion of a long-acting cylinder that slowly releases the agent (Viadur). The manufacturer's instructions should be followed.
- 7.3.6 Toxicity: Consult the package insert for comprehensive toxicity information. Class-related toxicity is generally a manifestation of the mechanism of action and related to low testosterone levels. In the majority of patients testosterone levels increase above normal in the first week, declining thereafter to baseline levels or below by the end of the second week of treatment. The most common side effect of LHRH analogs is vasomotor hot flashes; edema, gynecomastia, bone pain, thrombosis, and gastrointestinal disturbances have occurred. Potential exacerbations of signs and symptoms during the first few weeks of treatment is a concern in patients with vertebral metastases and/or urinary obstruction or hematuria which, if aggravated, may lead to neurological problems such as temporary weakness and/or paresthesia of the lower limbs or worsening of urinary symptoms. Other side effects include impotence and loss of libido, weight gain, depression, dizziness, loss of bone density, anemia, increased thirst and urination, unusual taste in the mouth, skin redness or hives, pain at injection site, and muscle mass and strength loss, hair changes, penile length and testicular volume loss, increased cholesterol, hypertension, diabetes exacerbation, emotional lability, nausea, vomiting, and rarely, allergic generalized rash and difficulty breathing.

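### Freedom from hormone therapy does not exclude protocol or prior ADT, and the time-to-event endpoints run from two different, undefined dates

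*Combined protocol and SAP*

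**What the plan says.** **FFHT.** Section 9.1.1 defines it as "The time from the date of treatment to first administration of androgen deprivation therapy". It is a named secondary endpoint (2.3.2.7) and appears again under the secondary aim in 12.2. No word in the definition limits which ADT counts.

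**ADT in this trial.** Every patient is to receive six months of it. Section 6.0: "RT will start ~2 months after the start of ADT when possible". Section 7.2: "The first LHRH administration will occur together with the start of anti-androgen treatment ~8 weeks prior to the start of RT". Section 7.0 also allows earlier exposure: "Some patients may have received prior hormonal therapy, but still require 6 months with the trial".

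**What may have been meant.** Section 2.3.3 says: "Disease specific endpoints will utilize a combination of laboratory values, multidisciplinary clinical decisions, radiographic imaging, functional imaging, and initiation of salvage therapy". This points towards later, salvage ADT, but it is a general sentence and does not amend the FFHT definition.

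**Time origins (9.1.1).** FFBR, FFLF, FFEPF, FFRF, FFDM and FFHT are timed from a treatment date. DFS, CSS and OS are timed from the date treatment is completed. The DFS events are BR, LF, EPF, RF, DM and death, so DFS shares its failures with the first group. Two further phrasings occur: the biopsy criterion for local failure counts two years from the start of treatment, and 12.3 estimates relapse-free probability 24 months after treatment.

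**What treatment consists of.** The Study Summary lists "2 brachytherapy implants, ~5-8 weeks of daily radiation, 6 months hormonal therapy". On order, section 6.0 says "Either Brachytherapy or EBRT can be delivered first", and it also allows the implants to be intercalated with EBRT. The two implants are "scheduled 1-2 weeks apart when possible" (6.1.1). Section 8.4 lets patients come off study treatment for several reasons.

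**The concern.** An endpoint meant to show how long patients stay free of hormone therapy cannot be computed if its event is the first ADT dose and ADT is the first planned treatment. The rule as stated picks up the trial's own drug, or a still earlier course.

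The split in origins raises two further problems. First, with a multi-part treatment in flexible order, two analysts could date the same relapse differently, and the DFS time of a relapse need not match its FFBR or FFDM time. Second, starting the DFS, CSS and OS clocks at completion conditions on having completed. A failure or death before that date has a negative or undefined time, and a patient who never completes has no origin at all. If such patients are left out, the loss is not neutral: it removes early failures and deaths and makes the three endpoints look better. Section 1.5 says the data are meant to lead to a phase III comparison of disease control and survival against palliative hormonal therapy, so these definitions should be reproducible.

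**Working it through.** The plan gives no figure for these endpoints, so there is none to reproduce. The check is a calendar of the possible origins.

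**Inputs**
- ADT start to RT start: about 8 weeks (7.2).
- Daily radiation: about 5-8 weeks, listed separately from the implants (Study Summary).
- First to second implant: 1-2 weeks (6.1.1).
- ADT duration: 6 months = 6 × 30.44 / 7 = 26.1 weeks (7.0, 7.2).

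**Weeks from first protocol ADT dose**
- RT start: 8.
- RT end, implants intercalated with EBRT: 8 + 5 = 13 to 8 + 8 = 16.
- RT end, implants and EBRT in sequence: 8 + 5 + 1 = 14 to 8 + 8 + 2 = 18, before any gap between components.
- ADT end: about 26.

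**Literal FFHT = (first ADT dose) − (treatment date)**

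| Treatment date taken as | FFHT |
|---|---|
| ADT start | 0 |
| RT start | about -8 weeks |
| RT end | about -13 to -18 weeks |

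Prior ADT, if counted, makes each value more negative.

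**A lenient reading does not rescue it.** Suppose the event is the first dose after the treatment date. From RT start, bicalutamide is taken daily until RT ends (7.1.5), so a protocol dose comes at once. From RT end, 26 − 18 = 8 to 26 − 13 = 13 weeks of the protocol course remain, and a planned LHRH dose could fall in that window, depending on the formulation.

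**Gap between the two origins**
- Both refer to the implants: 1-2 weeks.
- Both refer to the RT course: 5 weeks (shortest, intercalated) to 8 + 2 = 10 weeks (longest, in sequence).
- Treatment includes ADT: up to about 26 weeks (ADT start to ADT end).

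Nothing in the text decides between these. The evaluability wording in 9.1.1 refers to brachytherapy; the Study Summary treats all components as the treatment.

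**Illustration for the 24-month relapse-free estimate.** The documents give no relapse rate, so assume a constant hazard and a 24-month probability S between 30% and 70%. Shifting the origin by d months while keeping the 24-month label gives S^(1 ± d/24).
- 5 weeks (d = 1.15): about 1-2 points.
- 10 weeks (d = 2.30): about 2-4 points.
- 26 weeks (d = 6): about 6-11 points.

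**The case against.** The best reply is that the intent is plain. The name of the endpoint and the salvage-therapy phrase in 2.3.3 both point to later ADT, and no analyst would report a column of zero or negative times. That is a fair account of FFHT's purpose, but the stated rule still needs a qualifier that appears nowhere, and the analyst would have to invent it. The intended origin cannot be inferred in the same way.

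It can also be said that the effect is small. PSA is scheduled at months 3, 6 and 12 and then every 6 months (8.3), so a gap of a few weeks is shorter than the assessment interval, and the endpoints are described in 24 patients with no powered hypothesis. For the shorter gaps this stands. It does not answer the patients who have no time zero, and it does not apply to FFHT, where every patient on the planned sequence is affected.

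Using different origins for different endpoints is not in itself an error. The fault is that neither origin is defined and that one of them depends on completing treatment.

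Several stronger readings are tempting but unsupported:
- A reader might infer that RT could precede ADT, so that FFHT would measure the wait for protocol ADT. Section 6.0 lets RT start earlier or later than the two-month target; it does not say before ADT.
- A reader might count each patient without an origin as 1/24 = 4.2 percentage points. That is a unit, not an effect: the documents give no expected number of non-completers, and with censoring a patient need not weigh 1/24.
- The option in 6.2.4 to postpone or abort concerns a single implant session and is weak evidence of non-completion. Section 8.4 is the relevant provision, and its item 8.4.1 covers patients who withdraw before treatment.
- The rule that two follow-up PSAs are needed for disease-control evaluability is a separate matter and no part of this point.

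**Conclusion.** The point holds. As written, FFHT cannot be estimated on the planned sequence, and no other section repairs it. DFS, CSS and OS lack a usable time zero for patients who fail, die or stop before completion, and they do not share an origin with the failure endpoints from which DFS is built.

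The size depends on what the two dates are taken to mean, and the ranges above rest on the approximate durations in the protocol with no gap between radiation components. The 26-week figure applies only if ADT counts as part of treatment. The bias from dropped patients is favourable in direction but cannot be sized from the documents.

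A reader might infer that the trial's main conclusion is at risk. It is not: the primary toxicity test, the sample size of 24 and the stage 1 stopping rule use none of these definitions. This is a correction that should be made to descriptive secondary endpoints.

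**What to change.** 1. Define the FFHT event as the first ADT given outside the protocol course and after enrolment.
2. Name one dated origin for all time-to-event endpoints and for the 24-month relapse-free estimate in 12.3, for example the first protocol treatment of any kind, and include every patient who starts treatment.
3. Leave the PSA-bounce window and the two-year biopsy criterion in 9.1.1 on their own stated clocks.

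The cost is wording only, with no added visits or patients. DFS, CSS and OS may look slightly less favourable, because events before completion would count. Durations lengthen by the size of the shift for every endpoint whose origin moves earlier. That includes the endpoints now timed from the treatment date, if that date was meant to be an RT or implant date.
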